Phase 1 and Phase 2 measures will be used to achieve **2 Specific Aims**:

Aim 1. *To assess the acute effects of MEM (0 vs. 20 mg) on measures of early auditory information processing (EAIP) in patients with mild-to-moderate severity AD.* Measures of PPI, MMN and ASSR will be assessed in 88 individuals with mild-to-moderate severity AD after placebo (PBO) and 20 mg MEM po, in a double-blind, randomized order cross-over design. **Hypothesis 1:** Assessed across the full cohort of patients, PPI, MMN and ASSR will be significantly greater after MEM vs. PBO. However, the response to MEM will be heterogeneous: the magnitude of this “MEM effect” (MEM minus PBO) will vary across the dependent measures, and across patients, with some patients demonstrating robust increases in EAIP measures after MEM, and other demonstrating little response or reduced EAIP performance.

Aim 2. *To determine the ability of MEM-induced alterations in EAIP in AD patients to predict their clinical response to MEM.* The magnitude of the “MEM effect” will be calculated for each patient and each EAIP measure. MEM treatment will be initiated and titrated to 10 mg bid in all patients. Clinical severity will be assessed at baseline, 8, 16 and 24 weeks using the ADAS-cog as a primary measure. Analyses will determine whether the MEM effect on some or all EAIP measures moderates the magnitude of the clinical response to MEM. **Hypothesis 2:** Patients exhibiting a larger “MEM effect” on EAIP measures will exhibit a more robust positive clinical response to MEM, compared to patients exhibiting a smaller MEM effect on EAIP measures. This hypothesis will be tested empirically for each of the primary EAIP measures, and for regression-derived composite scores from multiple EAIP measures.

Analyses (linear mixed-effects model) will test the hypothesis (H2) that EAIP MEM sensitivity (in Phase 1) predicts the clinical response to MEM (in Phase 2). Moderating roles of specific variables on MEM sensitivity will be assessed, including demographic/clinical variables, baseline neuropsychological measures and genotypes associated with MEM sensitivity or AD. Source localization will identify anatomical substrates associated with MEM effects on EAIPs, and enable us to test structure- and circuit-based mediation models.

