Enhancing treatment effectiveness by using predictive biomarkers: Four medications are approved for the treatment of AD worldwide: three cholinesterase inhibitors (AChE-I's) and the noncompetitive *N*-methyl-D-aspartate (NMDA) receptor antagonist, memantine (MEM) (as well as a combination of an AChE-I + memantine). MEM is approved for treatment of moderate-to-severe AD, though it is frequently used in earlier stages of AD and even in Mild Cognitive Impairment (MCI) (86). A retrospective analysis of 5200 patients with newly diagnosed AD started on monotherapy, MEM was initiated in roughly 16% of these patients, and 1-year discontinuation rates and subsequent non-adherence rates were the lowest among all treatments (including 3 AChE-I's) (4). MEM's mechanisms of action are not well understood, but may include its ability to reduce glutamate-mediated neurotoxicity (66). While meta-analyses have confirmed that MEM monotherapy reduces cognitive impairment (3,14,93,119) and behavioral disturbances (40-1) in AD, these salutary effects are generally modest in magnitude and duration. Moreover, the clinical response to MEM is highly heterogeneous, with many AD patients showing little or no gains even with an extended MEM trial (14).

Both AD and MCI are heterogeneous in terms of presumed etiologies and symptom profiles (9,11). One way to enhance treatment efficacy is to narrow the target population from a broader, heterogeneous patient group to more selective "sensitive" clinical subgroups, identified through the use of laboratory-based biomarkers. In this approach to "precision medicine", biomarkers are used to stratify patients into subgroups for whom a medication would be more vs. less likely to be effective. Conceivably, a biomarker predicting MEM sensitivity could identify AD patients for whom MEM would be most protective against the progression of cognitive and behavioral disturbances; conversely, patients lacking a positive biomarker response might be counseled towards other treatments, to avoid the loss of time and resources at a critical phase of illness progression.

Fig. 1. Schematic showing the idealized impact of adding a biomarker to a heterogeneous population defined by a clinical phenotype to enhance the likelihood of treatment response.
 i = treatment-sensitive patient.

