Aim 1: Repeated measure (Rm)-ANOVAs will determine whether PPI, MMN and ASSR significantly differ after MEM vs. PBO (Hypothesis 1). Primary variables for each EAIP, as well as exploratory "secondary" measures, are identified above. Based on a recruited sample of 88 total participants, we will have 80% power to detect effect sizes of $d = 0.35$ (small) using a Bonferroni corrected $\alpha = .05/3$ (2-tail). Heterogeneity of response will be characterized using variance components expressed as intraclass correlation coefficients (ICCs).

Aim 2: Linear mixed-effects models regressing change in ADAS-cog outcome scores (at 8, 16, and 24 weeks vs. baseline) onto a fixed effect of group defined by MEM sensitivity will test the hypothesis that patients exhibiting a larger "MEM effect" on EAIP measures will exhibit a larger positive clinical response to MEM. Groups will be defined by a median split of "MEM effect" (MEM minus PBO) on EAIP. Power was estimated using methods described by Hedeker et al. (25) solving for sample size with $\alpha = .05$ (2-tail), test-retest correlations of .50, and 5% attrition at each time point. A sample of 88 total participants provides us with 80% power to detect a medium effect of $d = 0.50$. The primary outcome will be chosen based on effect sizes obtained as part of Aim 1. In exploratory analyses, we will also examine group by time interactions using orthogonal polynomial contrasts. We will also predict change in clinical outcomes as a function of all four candidate biomarkers in order to create an optimal prediction equation. We will perform ROC curve analyses using EAIP MEM sensitivity values as continuous variables and predict clinical improvement after MEM as a discrete outcome (responders vs. non-responders) in order to determine the clinical utility of this approach defined in terms of sensitivity and specificity. Secondary analyses will also be conducted with biomarker groups defined as "MEM-sensitive vs. -insensitive" via specific thresholds for EAIP MEM sensitivity.

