Why no “control” group? Two potential “control” groups are not included in this design. First, no parallel HS group is included to confirm the predicted effect of MEM on EAIP measures during laboratory testing. Because such findings in HS have already been reported by our group, and extended in various forms by other groups (discussed above), we view a re- replication as unjustifiable in terms of effort or cost, particularly because the outcome of HS testing would not directly alter the interpretation of the key results (prediction of clinical response in AD patients). Second, no parallel AD treatment group is proposed. Thus, it is conceivable that the EAIP response to MEM might reflect a degree of neuroplasticity or other biological characteristic within AD-relevant brain substrates, that is a *general predictor* of a positive clinical response to other drugs, eg. AChE-I’s, rather than a *specific predictor* of a therapeutic response to MEM. While we considered this possibility, we felt that the most cost-effective and biologically parsimonious approach was to test whether EAIP MEM sensitivity predicts clinical MEM sensitivity; a positive finding might justify studies in a future application, testing similar predictive value in combined regimens (MEM+AChE-I) as well as AChE-I monotherapy.

FOA-specific information: The use of MEM in AD has been the focus of many large multi-site studies; this application will not broadly address MEM’s therapeutic role, i.e. its mechanism of action, the role of NMDA in

AD pathogenesis, or the predicted optimal disease stage for MEM use. The focus of this application is to test the predictive value of EAIP MEM sensitivity on its therapeutic impact in AD. Justification for experimental parameters is provided above, including treatment dose, duration and target population; we do not propose fundamental studies of MEM's clinical effects, eg. pharmacodynamics, because these are well established, though we plan to store blood for future tests of potential predictive biomarkers. Our plans for future clinical development are described briefly above, and include: 1. Tests that include patients using combination regimens (MEM + AChE-I); 2. Tests with patients at earlier stages of illness; 3. Tests with other AD therapeutics for which an acute EAIP-based laboratory biomarker is available.

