- 1. All subjects receive treatment with the same FDA-approved treatment** for AD (memantine (MEM)) using a dose titration schedule that is consistent with common clinical practice. Thus, the **treatment phase is not blinded**, and thus there is no opportunity to utilize a DSMB for purposes related to study blinding or unblinding;
- 2. All adjustments to MEM dose and other medications are done by the treating physician, based on the clinical needs of the patient, and are not constrained by experimental design;**
- 3. No placebo control or other patient comparison group** is utilized: analyses rely on groups distinguished by biomarkers identified prior to initiation of MEM therapy;
- 4. The study is not designed to test the therapeutic benefits of MEM in AD per se**, as this issue has already been repeatedly addressed in large, multi-site clinical trials.

While the proposed therapeutic intervention is not experimental, and has had longstanding FDA approval in AD, this application nonetheless meets NIH criteria for a “Clinical Trial”, defined in “Notice of Revised NIH Definition of ‘Clinical Trial’”. Thus, a DSMP is described below, and a DSMB is available through faculty within the UCSD ADCS. Plans for implementing this DSMB, should this application be funded, are described below and in a supportive letter from the ADCS faculty (attached).

Potential Risks

The potential risks to study participants include:

- 1. Venopuncture:** During the initial assessment phase, blood will be collected for assessing patient's health status, and for study-related genetic markers. With any venopuncture procedure, there may be temporary slight discoloration of the skin.

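### H2 is worded as moderation of the response to memantine, but with every patient treated a positive result cannot separate greater drug benefit from slower natural decline

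*Combined protocol and SAP*

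**What the plan says.** Aim 2, in the Specific Aims and again under C. Approach, states: "Analyses will determine whether the MEM effect on some or all EAIP measures moderates the magnitude of the clinical response to MEM". The Abstract and Specific Aims describe the goal as a predictive biomarker that sorts patients into MEM-sensitive and MEM-insensitive before treatment.

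The design gives the drug to everyone: "MEM treatment will be initiated and titrated to 10 mg bid in all patients". The Data and Safety Monitoring Plan confirms this: "No placebo control or other patient comparison group".

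The Aim 2 analysis, under Statistical tests for each hypothesis, regresses ADAS-cog change at weeks 8, 16 and 24 "onto a fixed effect of group defined by MEM sensitivity will test the hypothesis". On the grouping it says: "Groups will be defined by a median split of" the MEM-minus-placebo EAIP difference. The same section plans ROC analyses to "predict clinical improvement after MEM as a discrete outcome (responders vs. non-responders").

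The answer to the question of why there is no control group acknowledges the gap: "Second, no parallel AD treatment group is proposed". The one alternative reading it discusses is that the marker might predict response to drugs in general, such as cholinesterase inhibitors, and not to MEM specifically.

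**The concern.** ADAS-cog change on open-label MEM is what the drug did plus what would have happened anyway. To show that a marker moderates a drug effect, one must compare treated with untreated outcomes at each marker level. The trial observes only the treated ones.

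The plan's own text makes the prognostic alternative plausible. At the end of A. Significance, an EAIP response is read as a sign that the relevant circuitry has been spared. The answer to whether Aim 2 depends on Aim 1 suggests that a missing response may reflect damage from the disease. Patients with more intact circuitry might decline more slowly with or without MEM.

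The section on why treatment lasts 24 weeks adds to this. It says treated patients are typically back at their starting level by week 24, and that the gain is delay relative to placebo patients. On that account, benefit at week 24 shows only against an untreated course, which this trial does not have.

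What is at stake is the central conclusion. After a significant H2, marker-low patients might have gained as much from MEM as marker-high patients and simply have been declining faster.

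**Working it through.** **1. The plan's power figure.** Inputs from the Aim 2 paragraph: N = 88, median split (44 per group), d = 0.50, two-sided alpha 0.05, correlation 0.50, 5% attrition per time point. I used the repeated-measures formula for a time-averaged difference over three visits, with retention 1, 0.95 and 0.9025:

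- Variance factor v = (1/9) × [1 + 1/0.95 + 1/0.9025 + 2 × 0.5 × (1/√0.95 + 1/√0.9025 + 1/√(0.95 × 0.9025))] = 0.702
- n per group = 2 × (1.960 + 0.842)² × 0.702 / 0.50² = 2 × 7.849 × 0.702 / 0.25 = 44.1
- Power at 44 per group = Φ(0.50 / √(2 × 0.702 / 44) − 1.960) = Φ(0.839) = 79.9%

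The stated figure reproduces. It is power for a difference between marker groups among treated patients.

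**2. What that difference contains.** Let U be mean untreated change and B mean drug benefit, both scored so that larger is better, with H and L for marker-high and marker-low. The H2 contrast estimates

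(U_H + B_H) − (U_L + B_L) = (U_H − U_L) + (B_H − B_L).

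The first bracket is prognostic and the second predictive. With only treated patients the data identify the sum and neither part. More treated patients would not change this.

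**3. Simulation of the contrast.** N = 88, three visits, correlation 0.5, 5% monotone dropout after each of the first two visits, 4,000 trials per row:

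| Prognostic part (SD) | Predictive part (SD) | H2 significant, all on MEM |
|---|---|---|
| 0 | 0 | 5% |
| 0.5 | 0 | 81% |
| 0 | 0.5 | 82% |
| 0.25 | 0.25 | 81% |
| 0.6 | −0.1 | 81% |

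In the last row marker-high patients gain less from the drug, and H2 is significant as often as in the other non-null rows.

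**4. How strong a prognostic link would be needed.** Assume identical drug benefit in everyone and a normally distributed marker with correlation r to natural ADAS-cog change. A median split turns r into a group difference of 2r√(2/π) = 1.596r in overall SD units. The plan's d = 0.50 then corresponds to r = 0.50 / 1.596 = 0.31. The documents give no value for r, so a range is shown:

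| r (assumed) | Group difference (SD) | Single visit, n = 88 | Three-visit average, correlation 0.50, no dropout |
|---|---|---|---|
| 0.1 | 0.16 | about 11% | about 15% |
| 0.2 | 0.32 | about 32% | about 45% |
| 0.3 | 0.48 | about 62% | about 80% |
| 0.4 | 0.64 | about 87% | about 98% |

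The three-visit column is nearer to the planned mixed model. It assumes that r holds at each visit.

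**5. What a direct test of moderation would take (illustration only).** With four equal cells (marker high or low, MEM or placebo) and an interaction of 0.50 SD, n per cell = 4 × 7.849 × 0.702 / 0.25 = 88.2, so 89 per cell and 356 in total. With 88 patients (22 per cell), power is Φ(0.50 / √(4 × 0.702 / 22) − 1.960) = Φ(−0.56), about 29%. In the simulation that interaction test was significant in 29% of trials for the purely predictive marker and 6% for the purely prognostic one, so it does tell them apart.

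**The case against.** The best defence is that the plan is open about its limits. It answers a call for pilot trials, says it is not designed to test whether MEM works, gives cost as a reason for having no parallel arm, often uses the milder word predicts, and treats a positive result as grounds for further study. All of that stands, and it is why the remedy is rewording and not redesign. It does not support the word moderates. Earlier trials established average efficacy, and nothing in the documents shows that they measured this marker, so they supply no untreated course by marker level.

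Nor does anything else in the design fill the gap. The Aim 1 placebo crossover isolates the acute effect on EAIP, not the untreated ADAS-cog course. Patients who stop MEM or add a cholinesterase inhibitor are self-selected and analysed separately. Baseline outcome and neuropsychological measures are explored as moderators, not used as adjusters in the H2 model.

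Practice effects are a weaker complaint. The plan uses alternate word lists and records prior assessments, and practice or expectancy biases the contrast only if it differs between marker groups.

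Three stronger readings are tempting but unsupported:

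- A reader might infer from the cited average effect (d = 0.3 at 8 weeks) that most responders on MEM would also have responded on placebo. That share depends on how a patient's outcomes on and off drug are related and on a responder cut-off. The documents give neither.
- A reader might take the remark in A. Significance that "patients lacking a positive biomarker response might be counseled towards other treatments" as a treatment rule drawn from this trial's ROC analysis. It is a hedged statement about what a valid marker could do, and it does not refer to the ROC results.
- A reader might conclude that the marker is prognostic. The documents make that plausible, but nothing in them shows it.

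**Conclusion.** The point holds. As worded, Aim 2 promises a property, moderation of a drug effect, that an all-treated design cannot establish, and the discussion of the missing control group leaves out the main rival explanation. The algebra needs no numerical assumption: H2 estimates the prognostic and predictive parts as one sum.

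The size of the risk does rest on assumptions. If the true prognostic link is weak (r near 0.1), a misleading positive is uncommon, at about 11 to 15% against a nominal 5%. At r near 0.3, a marker unrelated to drug benefit would produce roughly the effect the trial is powered to find.

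The study can still answer a useful question, namely whether the EAIP response to a MEM challenge is associated with subsequent change on MEM. The sample size calculation is sound for that question.

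**What to change.** 1. **Reword the claim.** In the Abstract, Specific Aims, C. Approach, the Aim 2 analysis paragraph and Multiple analytic strategies, restate H2 and the ROC aim as the association of the EAIP MEM effect with ADAS-cog change during MEM treatment, which may be prognostic or predictive. Reserve moderates and predictive for a later study with a concurrent comparison arm. In the control-group discussion, add that a prognostic explanation cannot be excluded.

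2. **Add a prespecified adjusted analysis.** Report H2 with and without adjustment for baseline severity already collected (for example baseline ADAS-cog or screening MMSE) and age.

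3. **Optional sensitivity analysis.** Add a pre-enrolment decline rate, (30 − screening MMSE) / years since onset, using the structured history. State its assumptions: a score of 30 at onset, linear decline and an accurately reported onset date. Note also that the MMSE is restricted to 10–22 by eligibility.

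The cost is text edits and one or two extra models on data already planned. Allocation, endpoints, visits and sample size do not change. The headline claim becomes weaker, and adjustment reduces the ambiguity but does not remove it.

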Alzheimer’s Disease (AD) is a severe neurodegenerative brain disorder, with limited therapeutic options. The low-affinity, voltage-dependent, uncompetitive NMDA receptor antagonist, memantine (MEM) is FDA-approved for treatment of moderate-to-severe AD; its mechanisms are not well understood, but may include a blunting of glutamate-mediated neurotoxicity. While meta-analyses confirm MEM’s effectiveness in delaying the progression of cognitive and behavioral disturbances in AD, the clinical response to MEM is modest, short-lived and highly heterogeneous, with many AD patients showing no gains even with an extended MEM trial. The utility of MEM in AD might be greatly enhanced if patients could be identified as “MEM-sensitive” vs. “MEM-insensitive” in advance of a therapeutic trial, using a **predictive biomarker**.

For the past decade, the PI has studied the acute neurophysiological effects of MEM in laboratory animals, healthy human subjects and schizophrenia patients. These studies demonstrated that a single “challenge dose” of MEM (20 mg) significantly enhanced laboratory measures of early auditory information processing (EAIP) in healthy subjects and schizophrenia patients: prepulse inhibition (PPI), mismatch negativity (MMN) and gamma band auditory steady-state response (ASSR; gamma power and synchronization). MEM-induced increases in these EAIP measures after one pill provides evidence that MEM is bioactive in cognition-relevant brain circuitry; *conceivably, such a brain “signal” might also identify individuals most likely to benefit from MEM’s therapeutic effects. This application tests whether the EAIP response to an acute MEM-challenge can predict a therapeutic response to MEM* in patients with mild-to-moderate AD, over a 24-week trial.

This application has two phases: 1. Biomarker assessment; and 2. Therapeutic trial. Phase 1 will test the acute effects of MEM (20 mg po) vs. placebo (PBO) on EAIP measures in 88 carefully characterized patients with mild-to-moderate severity AD who are not currently taking AD medications. From this “challenge” test, a set of “EAIP MEM sensitivity” measures will be derived for each patient. In Phase 2, all patients will begin an open-label trial of MEM monotherapy, titrated to 10 mg bid, with outcome measures collected after 8, 16 and 24 weeks of treatment. Medication adjustments are not restricted, and response heterogeneity is anticipated.

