parallels the use of a test-dose to predict clinical benefits from treatments ranging from hormones (7) to anti-Parkinsonian drugs (34) to bronchodilators (20). Evidence for enhanced EAIP in response to MEM challenge suggests that MEM is accessing neural circuitry relevant to neurocognition, and furthermore, that such circuitry has yet been spared, and remains plastic and hence a viable target for pharmacotherapy. Conceivably, via this approach, in the span of two office visits separated by one week (see "Methods") subgroups of AD patients will be stratified as "MEM-sensitive" vs. "MEM-insensitive", based on their physiological responses (eg. gain in EAIP) to an acute MEM challenge-dose. This "personalized medicine" approach has been used in other fields (7,20,34) and attempted for some psychotherapeutics (cf. 19,22), but has not yet been developed for AD.

[figure not shown]
B. Innovation: The primary innovation in this application is the *development of a clinically feasible test to predict sensitivity to the therapeutic response to MEM in AD patients based on the "biomarker" of MEM-enhanced EAIP*. As described in the PAR, "mediators of the therapeutic intervention" will also be identified.

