EEG data are continuously recorded from 64 channels using a BioSemi ActiveTwo system with a sampling rate of 1 kHz. Subjects are assessed on EEG biomarkers in the same order: MMN/P3a/RON (20 min), ASSR (5 min). Auditory stimuli are presented at 85 dB SPL via insert earphones. All setup and data acquisition take < 60 min with breaks. Stimulation, recording and analysis techniques for MMN are as in (57,99), using binaural stimulation (1 kHz square wave stimuli, 5 ms rise/fall) with fixed stimulus onset-to-onset asynchrony of 500 ms. A pseudorandom sequence of tones, of which 82% are standards (50 ms, 1000 Hz) and 18% are deviants (6% per deviant type): duration deviants are 100 ms, 1000 Hz; frequency deviants are 50 ms, 1500 Hz; double-oddball deviants are 100 ms, 1500 Hz. **MMN, P3a** and **RON** metrics are extracted as per (84,99) (**primary measures: μ V at Fz, 135-205 ms, 250-300 ms and 350-450 ms, respectively**). For **ASSR**, gamma evoked power and phase locking are assessed in response to 250 1-ms clicks presented in 500-ms trains at a frequency of 40Hz, played with an inter-train interval of 1-s, as per (39,49,59). Evoked power (**primary measure: mean μ V² at Fz (0-500 ms)**) and phase locking (**primary measure: mean PLF (0-500 ms)**) are calculated using wavelet transformation of the segmented data across the 30-50 Hz frequency layer, as per (59). Exact Low Resolution Electromagnetic Tomography Analyses (eLORETA) uses voxel-by-voxel comparisons to localize significant drug effects on ERP neural sources, as per (109,124).

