Analyses to test H2 will also utilize primary, secondary and exploratory metrics of **MEM's clinical effects**:

1. **primary** outcome measure: ADAS-cog, change from baseline;
2. **secondary** outcome measures: NPI-Q and Geriatric Depression Scale (change from baseline);
3. **exploratory** outcome measures: ADAS-cog factor-derived subscales (change from baseline) (eg. 81).

Factors that moderate the relationship of the primary biomarkers (EAIP MEM sensitivity) and clinical outcome will also be explored, including: 1. Genetic markers (GRIN, APOE, described above); and 2. Patient characteristics (eg. age; past AD medications; baseline (T0) neuropsychological and outcome measures).

Lastly, we will probe the specific anatomical basis of MEM effects on MMN and ASSR using **source locali-**

zation techniques (109,124); conceivably, these analyses will provide information more generally relevant to the anatomical basis for MEM's therapeutic actions, i.e. the "mediators of the therapeutic intervention", as described in this PAR. A simple model for such mediation might be: "MEM action on 'structure X' → EAIP change → enhanced therapeutic sensitivity," but more complex, circuit-based models will also be explored.

For simplicity, this application associates greater "EAIP MEM sensitivity" with an EAIP-enhancing response to MEM challenge (eg. EAIP (MEM minus PBO) > median value); this approach is parsimonious because arithmetically larger EAIP values are generally associated with positive neurocognitive and functional change (21,56,58,64,111). However, one might rationally argue that *any significant change in response to MEM challenge reflects "MEM sensitivity", and thus directionality of the MEM response should not be assumed*. Thus, while we represent arithmetically larger MEM responses as "MEM-sensitive" in this application, Aim 2 analyses (linear mixed-effects model) make no assumptions of directionality; exploratory categorical analyses will also define "MEM sensitivity" based on the absolute change in EAIP amplitude (i.e., positive or negative).

Important questions related to experimental design and analysis:

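### The plan promises to test or identify mediators of memantine's therapeutic effect, but the single-arm treatment phase and pre-therapy EEG cannot estimate any mediated effect of the 24-week therapy

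*Combined protocol and SAP*

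**What the plan says.** Three places make the claim, with different force.

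- Specific Aims, in the paragraph on the H2 analysis: "Source localization will identify anatomical substrates associated with MEM effects on EAIPs, and enable us to test structure- and circuit-based mediation models".
- B. Innovation: mediators of the therapeutic intervention, a phrase taken from the funding announcement, "will also be identified".
- Secondary / Exploratory Analyses: a simple chain runs from memantine's action on some structure X, through "EAIP change → enhanced therapeutic sensitivity", "but more complex, circuit-based models will also be explored". The passage offers this as possible information on the anatomical basis of memantine's therapeutic action, and names MMN and ASSR as the measures to be localised.

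The design facts that bear on the claim are these.

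- Specific Aims: "In Phase 2, all patients will begin an open-label trial of MEM monotherapy, titrated to 10 mg bid".
- Data and Safety Monitoring Plan: "No placebo control or other patient comparison group" is used. The answer to *Why no control group?* and Protection Against Study Risks agree.
- Intervention: therapy begins after EAIP testing is finished.
- Outcome measures: weeks 8, 16 and 24 list the ADAS-cog, NPI-Q and Geriatric Depression Scale. No repeat EEG or EAIP session is listed.
- Detailed Methods: eLORETA, applied to the EEG, "uses voxel-by-voxel comparisons to localize significant drug effects on ERP neural sources". MMN and ASSR come from the same 64-channel session. PPI is an EMG blink measure.

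The statistical sections give no estimand, model, assumptions or power for mediation.

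**The concern.** A mediator of a treatment carries part of that treatment's effect on an outcome. To estimate it, the treatment has to vary, and the mediator has to be measured after treatment begins and before the outcome. Neither condition is met for the 24-week therapy. ADAS-cog change on memantine is drug response plus natural course, and nothing in Phase 2 separates the two.

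What is at stake is interpretation. If a source-to-EAIP-to-outcome path reached significance, the present wording would allow it to be reported as a mechanism of memantine's benefit. The same path could arise because patients with better-preserved auditory circuitry both respond more to the challenge and decline more slowly on any treatment.

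**Working it through.** **The plan's own figures.** None is given for mediation. The nearest are the power statements, and both reproduce, so the sample size is not in question here.

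- Aim 1: paired t test, n = 88, d = 0.35, α = 0.05/3 two-sided. Power is 0.798 against a stated 80%.
- Aim 2: two groups of 44, d = 0.50, correlation 0.50, three follow-ups. A patient with t visits carries information t/(1 + 0.5(t − 1)), that is 1, 1.333 or 1.5.
  - Retention 1, 0.95, 0.9025: mean information 0.05(1) + 0.0475(1.333) + 0.9025(1.5) = 1.467. Power = Φ(0.5√(44 × 1.467/2) − 1.96) = 0.811.
  - Attrition starting before week 8: power is 0.791. Stated: 80%.

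**Step 1: is an effect of therapy estimable?** Regress ADAS-cog change on an intercept, treatment and EAIP change. Treatment equals 1 for all 88 patients, so its column repeats the intercept and the design matrix has rank 2 of 3. The treatment coefficient does not exist, and so there is no total, direct or indirect effect of therapy. Dose, adherence and added drugs may differ between patients in Phase 2, but by clinical decision and not by randomisation, so they supply no usable contrast.

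**Step 2: time order.** The documented sequence is screening and baseline ADAS-cog, two challenge days with EEG, start of therapy, titration, then clinical scales at weeks 8, 16 and 24. The EAIP change is fixed before therapy begins. It can predict or moderate the response to therapy; it cannot lie between therapy and outcome.

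**Step 3: can the path separate drug response from prognosis?** Assumed values, for illustration only. U is a latent prognostic factor, S the acute EEG signal with S = 0.5U + √0.75·e, source = S + 0.5e and scalp = 0.8S + 0.5e, with independent errors.

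- World A, the drug does nothing clinically: Y = 0.6U + 0.8e, so cov(S, Y) = 0.5 × 0.6 = 0.30.
- World B, drug response drives outcome: Y = 0.3S + 0.95e, so cov(S, Y) = 0.30.

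In both worlds:

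- source-to-scalp slope a = 0.8/1.25 = 0.64;
- scalp-to-outcome slope adjusted for source b = (1.25 × 0.24 − 0.8 × 0.30)/(1.25 × 0.89 − 0.8²) = 0.06/0.4725 = 0.127;
- indirect path ab = 0.081.

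In 2,000 simulated trials of 88, the joint-significance test was positive in 11.2% of runs in world A and 10.1% in world B, with mean indirect paths of 0.078 and 0.077. The values were chosen so that the covariances match. The point is that such a match is possible and the planned data could not reveal it.

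**Step 4: the first arrow.** For MMN and ASSR, the source estimate and the scalp value are summaries of one recording in one session. The randomised cross-over estimates memantine's acute effect on each. It cannot show that the first precedes the second.

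**The case against.** The strongest reply is that the chain in Secondary / Exploratory Analyses does not start from assignment to 24 weeks of therapy. It starts from the response to the challenge dose, which is randomised within patient and precedes the outcome, and it ends in differences between patients in response. The Specific Aims sentence also speaks of effects on EAIP and does not itself name the therapeutic effect. This stands in part: acute effects are estimable, and an association of acute response with later outcome is a legitimate question. It does not rescue the claim, because the chain's last term is therapeutic sensitivity, which is not observed apart from prognosis, and the Innovation sentence is explicit about the therapeutic intervention.

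The plan also hedges. The models are exploratory, the FOA-specific section says mechanism of action will not be broadly addressed, and the control-group answer concedes that the biomarker may be a general rather than memantine-specific predictor. That limits the weight of the point, but the concession is never carried over to the mediation claim.

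A reader might infer more than the documents support:

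- **That source and scalp measures are near-copies, so a significant indirect path is almost automatic.** The documents give no correlation. Scalp MMN and evoked power are read at Fz, while eLORETA gives voxel estimates. High correlation would also work the other way. If source and scalp each correlate 0.3 with outcome and r with each other, the adjusted scalp slope is 0.3/(1 + r) and its variance inflates by 1/(1 − r²). In simulation at n = 88 the path was significant in 47%, 23%, 10% and 7% of runs at r = 0.3, 0.7, 0.9 and 0.95.
- **That the shared recording affects every EAIP measure.** PPI is EMG and is not among the measures named for localisation.
- **That an association analysis is missing.** The text on exploratory EAIP measures already plans to localise the memantine-induced changes that best predict clinical response.

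**Conclusion.** The point holds as an over-claim in a secondary analysis. Mediation of memantine's therapeutic effect is not identifiable in this design: 0 of 88 patients contribute a treatment contrast on ADAS-cog, and the proposed mediator is measured only before therapy. These two findings follow from the documented design and need no numerical assumption. The 10–11% figures do rest on assumed parameters and serve only as illustration. For MMN and ASSR the order of source and scalp change also cannot be established; the strength of their correlation is unknown.

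A reader might take this as a flaw in the main hypotheses. The documents do not support that. H1 rests on the randomised cross-over, and H2 asks whether EAIP change predicts outcome on memantine; neither needs a mediation claim.

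**What to change.** - In B. Innovation, delete the sentence promising that mediators will be identified.
- In Specific Aims and in Secondary / Exploratory Analyses, delete the mediation models and the structure-X chain.
- Keep the localisation of acute memantine effects in the randomised cross-over, and the planned analysis of which localised memantine-minus-placebo changes predict ADAS-cog change. Report the latter as exploratory association with outcome on memantine.
- State the voxel-wise multiplicity control. The plan refers to cited methods papers, so whether they include it cannot be judged from the documents.
- Add a sentence that mediation of therapeutic benefit is not testable in this single-arm phase.

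The cost is wording, fewer exploratory models and one claim made to the funder. No patients, data or power are lost. Keeping the claim would instead require a concurrent comparator, EEG or EAIP measured during therapy before the outcome, and a stated mediation estimand with its assumptions. The documents do not allow a sample size to be computed for that.
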